**Figure 4. Maximum Local Reactogenicity, by Treatment Assignment**

Boxplots of local reactogenicity events defined as specific surveyed adverse events that are commonly associated with infusion administration and that have an onset within 3 days following an infusion. Local reactogenicity events assessed in this study are: local pain to the infusion site, local tenderness to the infusion site, erythema at the infusion site, and induration/swelling at the infusion site. Severity definitions are based on The Division of AIDS Table for Grading the Severity of Adult and Pediatric Adverse Events (DAIDS AE Grading Table), Version 2.0 (January 2010).

**HVTNxxx/HPTNxxx:  
Closed DSMB Report for DSMB meeting on [Date].  
Data Cutoff date:[Date].**

**Figure 5: Maximum Systemic Reactogenicity, by Treatment Assignment**

Boxplots of systemic reactogenicity events defined as specific surveyed adverse events that are commonly associated with infusion administration and that have an onset within 3 days following an infusion. Systemic reactogenicity events are: malaise and/or fatigue, myalgia, headache, nausea, vomiting, chills, arthralgia and body temperature. Severity definitions are based on The Division of AIDS Table for Grading the Severity of Adult and Pediatric Adverse Events (DAIDS AE Grading Table), Version 2.0 (January 2010).

**HVTNxxx/HPTNxxx:  
 Closed DSMB Report for DSMB meeting on [Date].  
 Data Cutoff date:[Date].**

**Table 8. Expedited Adverse Experiences (EAEs) Reported to the Regulatory Support Center (RSC) by Treatment Assignment, Participant and Decreasing Severity NOTE: \* in column 'Non Rept.' indicates non-reportable EAE by DAIDS criteria, as determined by RSC.**

Trt.	Publication ID	Severity	EAE Number	Adverse Experience	Onset Date	Relation to Study Product	Medical Officer's Relation to Study Product	Number of Previous Infusions	Days Since Last Infusion	Non Reportable
A	XXX-XXXX	text	XXXXXX	text	dd-MMM-yyyy	text	text	X	XX	
	XXX-XXXX	text	XXXXXX	text	dd-MMM-yyyy	text	text	X	XX	
B	XXX-XXXX	text	XXXXXX	text	dd-MMM-yyyy	text	text	X	XX	
	XXX-XXXX	text	XXXXXX	text	dd-MMM-yyyy	text	text	X	XX	
C	XXX-XXXX	text	XXXXXX	text	dd-MMM-yyyy	text	text	X	XX	
	XXX-XXXX	text	XXXXXX	text	dd-MMM-yyyy	text	text	X	XX	
	XXX-XXXX	text	XXXXXX	text	dd-MMM-yyyy	text	text	X	XX	
	XXX-XXXX	text	XXXXXX	text	dd-MMM-yyyy	text	text	X	XX	

**HVTNxxx/HPTNxxx:  
Closed DSMB Report for DSMB meeting on [Date].  
Data Cutoff date:[Date].**

**Table 9. Adverse Events (AEs) by System Organ Class and Severity and Treatment Assignment Sorted by Decreasing Frequency**

System Organ Class/ Severity	Total			A			B			C		
	(N=XXXX) n	(%)		(N=XXXX) n	(%)		(N=XXXX) n	(%)		(N=XXXX) n	(%)	
Participants with one or more AEs												
Mild and Greater	xxx	(xx.x%)	xxx	(xx.x%)	xxx	(xx.x%)	xxx	(xx.x%)	xxx	(xx.x%)	xxx	(xx.x%)
Moderate and Greater	xxx	(xx.x%)	xxx	(xx.x%)	xxx	(xx.x%)	xxx	(xx.x%)	xxx	(xx.x%)	xxx	(xx.x%)
Severe and Greater	xxx	(xx.x%)	xxx	(xx.x%)	xxx	(xx.x%)	xxx	(xx.x%)	xxx	(xx.x%)	xxx	(xx.x%)
Life Threatening and Greater	xxx	(xx.x%)	xxx	(xx.x%)	xxx	(xx.x%)	xxx	(xx.x%)	xxx	(xx.x%)	xxx	(xx.x%)
Fatal	xxx	(xx.x%)	xxx	(xx.x%)	xxx	(xx.x%)	xxx	(xx.x%)	xxx	(xx.x%)	xxx	(xx.x%)
Infections and infestations												
Mild and Greater	xxx	(xx.x%)	xxx	(xx.x%)	xxx	(xx.x%)	xxx	(xx.x%)	xxx	(xx.x%)	xxx	(xx.x%)
Moderate and Greater	xxx	(xx.x%)	xxx	(xx.x%)	xxx	(xx.x%)	xxx	(xx.x%)	xxx	(xx.x%)	xxx	(xx.x%)
Severe and Greater	xxx	(xx.x%)	xxx	(xx.x%)	xxx	(xx.x%)	xxx	(xx.x%)	xxx	(xx.x%)	xxx	(xx.x%)
Life Threatening and Greater	xxx	(xx.x%)	xxx	(xx.x%)	xxx	(xx.x%)	xxx	(xx.x%)	xxx	(xx.x%)	xxx	(xx.x%)
Fatal	xxx	(xx.x%)	xxx	(xx.x%)	xxx	(xx.x%)	xxx	(xx.x%)	xxx	(xx.x%)	xxx	(xx.x%)
Gastrointestinal disorders												
Mild and Greater	xxx	(xx.x%)	xxx	(xx.x%)	xxx	(xx.x%)	xxx	(xx.x%)	xxx	(xx.x%)	xxx	(xx.x%)
Moderate and Greater	xxx	(xx.x%)	xxx	(xx.x%)	xxx	(xx.x%)	xxx	(xx.x%)	xxx	(xx.x%)	xxx	(xx.x%)
Severe and Greater	xxx	(xx.x%)	xxx	(xx.x%)	xxx	(xx.x%)	xxx	(xx.x%)	xxx	(xx.x%)	xxx	(xx.x%)
Life Threatening and Greater	xxx	(xx.x%)	xxx	(xx.x%)	xxx	(xx.x%)	xxx	(xx.x%)	xxx	(xx.x%)	xxx	(xx.x%)
Fatal	xxx	(xx.x%)	xxx	(xx.x%)	xxx	(xx.x%)	xxx	(xx.x%)	xxx	(xx.x%)	xxx	(xx.x%)
General disorders and administration Country conditions												
Mild and Greater	xxx	(xx.x%)	xxx	(xx.x%)	xxx	(xx.x%)	xxx	(xx.x%)	xxx	(xx.x%)	xxx	(xx.x%)
Moderate and Greater	xxx	(xx.x%)	xxx	(xx.x%)	xxx	(xx.x%)	xxx	(xx.x%)	xxx	(xx.x%)	xxx	(xx.x%)
Severe and Greater	xxx	(xx.x%)	xxx	(xx.x%)	xxx	(xx.x%)	xxx	(xx.x%)	xxx	(xx.x%)	xxx	(xx.x%)
Life Threatening and Greater	xxx	(xx.x%)	xxx	(xx.x%)	xxx	(xx.x%)	xxx	(xx.x%)	xxx	(xx.x%)	xxx	(xx.x%)
Fatal	xxx	(xx.x%)	xxx	(xx.x%)	xxx	(xx.x%)	xxx	(xx.x%)	xxx	(xx.x%)	xxx	(xx.x%)
Respiratory, thoracic and mediastinal disorders												
Mild and Greater	xxx	(xx.x%)	xxx	(xx.x%)	xxx	(xx.x%)	xxx	(xx.x%)	xxx	(xx.x%)	xxx	(xx.x%)

N's are the number of participants enrolled.  
n's are the number of participants reporting one or more AEs within a specific system organ class.  
Incidence is calculated by n divided by the number enrolled x 100.  
AE records included in the table have been coded into MedDRA codes by SCHARP clinical staff.

**HVTNxxx/HPTNxxx:  
Closed DSMB Report for DSMB meeting on [Date].  
Data Cutoff date:[Date].**

**Table 10. Grade 3-5 Adverse Events (AEs) by High Level Term and Severity and Treatment Assignment, Sorted by Decreasing Frequency**

	Total (N=XXXX) n (%)	A (N=XXXX) n (%)	B (N=XXXX) n (%)	C (N=XXXX) n (%)
Participants with one or more AEs				
Severe and Greater	xxx (xx.x%)	xxx (xx.x%)	xxx (xx.x%)	xxx (xx.x%)
Life Threatening and Greater	xxx (xx.x%)	xxx (xx.x%)	xxx (xx.x%)	xxx (xx.x%)
Fatal	xxx (xx.x%)	xxx (xx.x%)	xxx (xx.x%)	xxx (xx.x%)
Poisoning and toxicity				
Severe and Greater	xxx (xx.x%)	xxx (xx.x%)	xxx (xx.x%)	xxx (xx.x%)
Life Threatening and Greater	xxx (xx.x%)	xxx (xx.x%)	xxx (xx.x%)	xxx (xx.x%)
Fatal	xxx (xx.x%)	xxx (xx.x%)	xxx (xx.x%)	xxx (xx.x%)
Abdominal and gastrointestinal disorders				
Severe and Greater	xxx (xx.x%)	xxx (xx.x%)	xxx (xx.x%)	xxx (xx.x%)
Life Threatening and Greater	xxx (xx.x%)	xxx (xx.x%)	xxx (xx.x%)	xxx (xx.x%)
Fatal	xxx (xx.x%)	xxx (xx.x%)	xxx (xx.x%)	xxx (xx.x%)
Streptococcal Infections				
Severe and Greater	xxx (xx.x%)	xxx (xx.x%)	xxx (xx.x%)	xxx (xx.x%)
Life Threatening and Greater	xxx (xx.x%)	xxx (xx.x%)	xxx (xx.x%)	xxx (xx.x%)
Fatal	xxx (xx.x%)	xxx (xx.x%)	xxx (xx.x%)	xxx (xx.x%)
Pain and discomfort NEC				
Severe and Greater	xxx (xx.x%)	xxx (xx.x%)	xxx (xx.x%)	xxx (xx.x%)
Life Threatening and Greater	xxx (xx.x%)	xxx (xx.x%)	xxx (xx.x%)	xxx (xx.x%)
Fatal	xxx (xx.x%)	xxx (xx.x%)	xxx (xx.x%)	xxx (xx.x%)
Viral infections NEC				
Severe and Greater	xxx (xx.x%)	xxx (xx.x%)	xxx (xx.x%)	xxx (xx.x%)
Life Threatening and Greater	xxx (xx.x%)	xxx (xx.x%)	xxx (xx.x%)	xxx (xx.x%)

N's are the number of participants enrolled.

n's are the number of participants reporting one or more AEs within a specific system organ class.

Incidence is calculated by n divided by the number enrolled x 100. AE records included in the table have been coded into MedDRA codes by SCHARP clinical staff.

HVTNxxx/HPTNxxx:  
 Closed DSMB Report for DSMB meeting on [Date].  
 Data Cutoff date:[Date].

**Table 11. Adverse Events (AEs) by High Level Term and Severity and Treatment Assignment, Sorted by Decreasing Frequency**

	Total (N=XXXX) n (%)	A (N=XXXX) n (%)	B (N=XXXX) n (%)	C (N=XXXX) n (%)
Participants with one or more AEs				
Mild and Greater	xxx (xx.x%)	xxx (xx.x%)	xxx (xx.x%)	xxx (xx.x%)
Moderate and Greater	xxx (xx.x%)	xxx (xx.x%)	xxx (xx.x%)	xxx (xx.x%)
Severe and Greater	xxx (xx.x%)	xxx (xx.x%)	xxx (xx.x%)	xxx (xx.x%)
Life Threatening and Greater	xxx (xx.x%)	xxx (xx.x%)	xxx (xx.x%)	xxx (xx.x%)
Fatal	xxx (xx.x%)	xxx (xx.x%)	xxx (xx.x%)	xxx (xx.x%)
Poisoning and Toxicity				
Mild and Greater	xxx (xx.x%)	xxx (xx.x%)	xxx (xx.x%)	xxx (xx.x%)
Moderate and Greater	xxx (xx.x%)	xxx (xx.x%)	xxx (xx.x%)	xxx (xx.x%)
Severe and Greater	xxx (xx.x%)	xxx (xx.x%)	xxx (xx.x%)	xxx (xx.x%)
Life Threatening and Greater	xxx (xx.x%)	xxx (xx.x%)	xxx (xx.x%)	xxx (xx.x%)
Fatal	xxx (xx.x%)	xxx (xx.x%)	xxx (xx.x%)	xxx (xx.x%)
Streptococcal Infections				
Mild and Greater	xxx (xx.x%)	xxx (xx.x%)	xxx (xx.x%)	xxx (xx.x%)
Moderate and Greater	xxx (xx.x%)	xxx (xx.x%)	xxx (xx.x%)	xxx (xx.x%)
Severe and Greater	xxx (xx.x%)	xxx (xx.x%)	xxx (xx.x%)	xxx (xx.x%)
Life Threatening and Greater	xxx (xx.x%)	xxx (xx.x%)	xxx (xx.x%)	xxx (xx.x%)
Fatal	xxx (xx.x%)	xxx (xx.x%)	xxx (xx.x%)	xxx (xx.x%)
Allergies to foods, food additives, drugs and other chemicals				
Mild and Greater	xxx (xx.x%)	xxx (xx.x%)	xxx (xx.x%)	xxx (xx.x%)
Moderate and Greater	xxx (xx.x%)	xxx (xx.x%)	xxx (xx.x%)	xxx (xx.x%)
Severe and Greater	xxx (xx.x%)	xxx (xx.x%)	xxx (xx.x%)	xxx (xx.x%)

N's are the number of participants enrolled.

n's are the number of participants reporting one or more AEs within a specific system organ class.

Incidence is calculated by n divided by the number enrolled x 100.

AE records included in the table have been coded into MedDRA codes by SCHARP clinical staff.

**HVTNxxx/HPTNxxx:  
Closed DSMB Report for DSMB meeting on [Date].  
Data Cutoff date:[Date].**

**Table 12. Adverse Events (AEs) Related to Study Product by High Level Term and Treatment Assignment**

High Level Term/Relationship	Total			A		B		C	
	(N=XXXX) n (%)	(N=XXXX) n (%)	(N=XXXX) n (%)	(N=XXXX) n (%)	(N=XXXX) n (%)	(N=XXXX) n (%)	(N=XXXX) n (%)		
Participants with one or more AEs									
Related	xx (xx.x%)	xx (xx.x%)	xx (xx.x%)	xx (xx.x%)	xx (xx.x%)	xx (xx.x%)	xx (xx.x%)	xx (xx.x%)	xx (xx.x%)
Viral Infections NEC									
Related	xx (xx.x%)	xx (xx.x%)	xx (xx.x%)	xx (xx.x%)	xx (xx.x%)	xx (xx.x%)	xx (xx.x%)	xx (xx.x%)	xx (xx.x%)
Gastrointestinal disorders									
Related	xx (xx.x%)	xx (xx.x%)	xx (xx.x%)	xx (xx.x%)	xx (xx.x%)	xx (xx.x%)	xx (xx.x%)	xx (xx.x%)	xx (xx.x%)
Poisoning and Toxicity									
Related	xx (xx.x%)	xx (xx.x%)	xx (xx.x%)	xx (xx.x%)	xx (xx.x%)	xx (xx.x%)	xx (xx.x%)	xx (xx.x%)	xx (xx.x%)
Allergies to foods, food additives, drugs and other chemicals									
Related	xx (xx.x%)	xx (xx.x%)	xx (xx.x%)	xx (xx.x%)	xx (xx.x%)	xx (xx.x%)	xx (xx.x%)	xx (xx.x%)	xx (xx.x%)
Mineral and Electrolyte Analyses									
Related	xx (xx.x%)	xx (xx.x%)	xx (xx.x%)	xx (xx.x%)	xx (xx.x%)	xx (xx.x%)	xx (xx.x%)	xx (xx.x%)	xx (xx.x%)
Bronchitis									
Related	xx (xx.x%)	xx (xx.x%)	xx (xx.x%)	xx (xx.x%)	xx (xx.x%)	xx (xx.x%)	xx (xx.x%)	xx (xx.x%)	xx (xx.x%)
Upper respiratory tract infection									
Related	xx (xx.x%)	xx (xx.x%)	xx (xx.x%)	xx (xx.x%)	xx (xx.x%)	xx (xx.x%)	xx (xx.x%)	xx (xx.x%)	xx (xx.x%)
Leukocytoses NEC									
Related	xx (xx.x%)	xx (xx.x%)	xx (xx.x%)	xx (xx.x%)	xx (xx.x%)	xx (xx.x%)	xx (xx.x%)	xx (xx.x%)	xx (xx.x%)

N's are the number of participants enrolled.

n's are the number of participants reporting one or more AEs within a specific system organ class.

Incidence is calculated by n divided by the number enrolled x 100.

AE records included in the table have been coded into MedDRA codes by SCHARP clinical staff.

**HVTNxxx/HPTNxxx:  
 Closed DSMB Report for DSMB meeting on [Date].  
 Data Cutoff date:[Date].**

**Table 13A. Distribution of Safety Laboratory Values, by Treatment Assignment**

	Total	A	B	C
ALT				
Infusion #1 (baseline)				
N	xxx	xxx	xxx	xxx
Median (IQR)	xxx (xxx – xxx)	xxx (xxx – xxx)	xxx (xxx – xxx)	xxx (xxx – xxx)
Min, Max	xxx, xxx	xxx, xxx	xxx, xxx	xxx, xxx
Median change from baseline (IQR)	xxx (xxx – xxx)	xxx (xxx – xxx)	xxx (xxx – xxx)	xxx (xxx – xxx)
Infusion #2				
N	xxx	xxx	xxx	xxx
Median (IQR)	xxx (xxx – xxx)	xxx (xxx – xxx)	xxx (xxx – xxx)	xxx (xxx – xxx)
Min, Max	xxx, xxx	xxx, xxx	xxx, xxx	xxx, xxx
Median change from baseline (IQR)	xxx (xxx – xxx)	xxx (xxx – xxx)	xxx (xxx – xxx)	xxx (xxx – xxx)
....				
Infusion #10				
N	xxx	xxx	xxx	xxx
Median (IQR)	xxx (xxx – xxx)	xxx (xxx – xxx)	xxx (xxx – xxx)	xxx (xxx – xxx)
Min, Max	xxx, xxx	xxx, xxx	xxx, xxx	xxx, xxx
Median change from baseline (IQR)	xxx (xxx – xxx)	xxx (xxx – xxx)	xxx (xxx – xxx)	xxx (xxx – xxx)
Hemoglobin				
.				
.				
.				

**HVTNxxx/HPTNxxx:  
 Closed DSMB Report for DSMB meeting on [Date].  
 Data Cutoff date:[Date].**

**Table 13B. Safety Laboratory Values Meeting Grade 1 AE Criteria or Above, by Treatment Assignment**

	Total	A	B	C
ALT				
Infusion #1	xxx (xx.x%)	xxx (xx.x%)	xxx (xx.x%)	xxx (xx.x%)
Infusion #2	xxx (xx.x%)	xxx (xx.x%)	xxx (xx.x%)	xxx (xx.x%)
...	...	...	...	...
Infusion #10	xxx (xx.x%)	xxx (xx.x%)	xxx (xx.x%)	xxx (xx.x%)
Hemoglobin				
Infusion #1	xxx (xx.x%)	xxx (xx.x%)	xxx (xx.x%)	xxx (xx.x%)
Infusion #2	...	...	...	...
...	xxx (xx.x%)	xxx (xx.x%)	xxx (xx.x%)	xxx (xx.x%)
Infusion #10	xxx (xx.x%)	xxx (xx.x%)	xxx (xx.x%)	xxx (xx.x%)
Platelets				
Infusion #1	xxx (xx.x%)	xxx (xx.x%)	xxx (xx.x%)	xxx (xx.x%)
Infusion #2	xxx (xx.x%)	xxx (xx.x%)	xxx (xx.x%)	xxx (xx.x%)
...	...	...	...	...
Infusion #10	xxx (xx.x%)	xxx (xx.x%)	xxx (xx.x%)	xxx (xx.x%)

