5.3.3 Discontinuing infusions for a participant

Under certain circumstances, an individual participant's infusions will be permanently discontinued. Specific events that will result in stopping a participant's infusion schedule include:

- Co-enrollment in a study with an investigational research agent (rare exceptions allowing for the continuation of infusions may be granted with the unanimous consent of the HVTN 704/HPTN 085 PSRT);
- Clinically significant condition (ie, a condition that affects the immune system or for which continued infusions and/or blood draws may pose additional risk), including but not limited to the following:
 - Any grade 4 local or systemic reactogenicity symptom or AE that is subsequently considered to be related to study product;
 - An SAE that is subsequently considered to be related to study product;
 - Any grade 3 clinical AE (exception: fever or vomiting and subjective local and systemic symptoms) that is subsequently considered to be related to study product;
 - Any grade 3 or 4 lab abnormality confirmed by a repeated value that is subsequently considered to be related to study product;
 - Clinically significant hypersensitivity reaction including but not limited to type 1 hypersensitivity reaction and/or serum sickness associated with study product. Consultation with the HVTN 704/HPTN 085 PSRT is required prior to subsequent infusion following any hypersensitivity reaction associated with study product; or
- Investigator determination in consultation with Protocol Team leadership (eg, for repeated nonadherence to study staff instructions).

Infusions will be permanently discontinued for a participant diagnosed with HIV infection or with 2 reactive HIV tests, even if subsequent testing indicates that the participant is not HIV infected.

Participants for whom infusions are discontinued for reasons other than HIV infection should be counseled on the importance of continuing with the study and strongly encouraged to participate in Schedule 4 follow-up visits and protocol-specified procedures (see Appendix I and Appendix M), unless medically contraindicated.

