- HIV infection assessment including pre-test counseling. A subsequent follow-up contact is conducted to provide post-test counseling and to report results to participant;
- Confirm that participants received HIV test results from previous visit. If not, provide test results and post-test counseling as appropriate;
- Behavioral risk assessment questionnaire;
- Assessment of new or unresolved social impacts (site staff will ask participant about the status of any unresolved social impacts and if s/he has experienced any new social impacts as a result of the trial participation);
- Blood collection for HIV testing, PrEP monitoring, CBC/differential, ALT, creatinine, VRC01 Ab levels, functional assays, and sample storage (see Appendix I and Appendix M);
- Urine dipstick (see Section 7.9);
- Urine or serum pregnancy test (for participants who are capable of becoming pregnant). Persons who are NOT capable of becoming pregnant due to having undergone total hysterectomy or bilateral oophorectomy (verified by medical records), are not required to undergo pregnancy testing; and
- Complete physical examination, including weight, vital signs, and clinical assessments of head, ears, eyes, nose, and throat; neck; lymph nodes; heart; chest; abdomen; extremities; neurological function; and skin.

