itudy product administration procedures	0						8											000000000000000000000000000000000000000			0						-
IV infusion ⁹	—	х	—	Х	—	—	X	-	х	—	X	—	х	—	х	—	x	—	х	—	х	—	—	—	—	—	-
Reactogenicity assessment ¹⁰	—	х	—	Х	—	—	x	 	х	—	x	—	х	—	х	—	x	—	х	—	x	—	—	—	—	—	-
Poststudy							00000											0		-	000000000000000000000000000000000000000		-				1
Unblind participant	_	_	_	1-	- 1	—	—	 	-	_	†	_	_	—	 	 	 	_	—	 	—	_	- 1	—	_	_	x

¹ Screening may occur over the course of several contacts/visits up to and including day 0 prior to infusion.

² For specimen collection requirements, see Appendix F.

³ Pregnancy prevention assessments are required only for participants who are capable of becoming pregnant.

⁴ Includes pre-test counseling and HIV testing. A subsequent follow-up contact is conducted to provide post-test counseling and to report results to participant.

⁵ For a participant capable of becoming pregnant, pregnancy test must be performed on the day of infusion prior to infusion. Pregnancy test to determine eligibility may be performed at screening, but must also be done on Day 0 prior to infusion. Presons who are NOT capable of becoming pregnant due to having undergone total hysterectomy or bilateral oophorectomy (verified by medical records), are not required to undergo pregnancy tests may be used to confirm the results of, or substitute for, a urine pregnancy test.

⁶ Syphilis testing will be done by serology.

⁷ Syphilis and Chlamydia/Gonorrhea testing will be performed at visits 2, 9 15, and 21; in addition, testing may occur at any visit or if clinically indicated.

⁸ Chlamydia/Gonorrhea testing will be done with urine and rectal swabs; oropharyngeal swabs will be collected for gonorrhea testing at visit 2; in addition, testing may occur at any visit if clinically indicated. A combination gonorrhea/chlamydia oropharyngeal test is allowable (see the SSP for results reporting).

⁹ Blood draws required at infusion visits must be performed prior to administration of study product; however, it is not necessary to have results prior to administration, except for results of a serum pregnancy test, if indicated. Lab tests must be drawn within the 3 days prior to infusion.

¹⁰ Reactogenicity assessments performed for 3 days postinfusion (see Section 7.10).

¹¹ And microscopy if needed.

¹² If HIV test results are not available at the visit indicated, provide test results at next available opportunity.

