### **7.1.3 Local Laboratory Values**

Box plots of local laboratory values will be generated for baseline values and for values measured during the course of the study by treatment arm and visit. Each box plot will show the first quartile, the median, and the third quartile. Outliers (values outside the box plot) will also be plotted. If appropriate, horizontal lines representing boundaries for abnormal values will be plotted.

For each local laboratory measure, summary statistics will be presented by treatment arm and timepoint, as well as changes from baseline for postenrollment values. In addition, the number (percentage) of participants with local laboratory values recorded as meeting Grade 1 AE criteria or above as specified in the DAIDS AE Grading Table will be tabulated by treatment arm for each postinfusion timepoint. Reportable clinical laboratory abnormalities without an associated clinical diagnosis will also be included in the tabulation of AEs described above.

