## Appendix A

Mock tables and figures for the DSMB Closed Report are included below. The Closed Report summarizes trial information pooled across the treatment groups (labeled Total) and by masked treatment assignment (labeled A, B, and C). At the request of the DSMB, protocol statisticians will unmask treatment labels. A subset of these tables and figures will

form the Open Report, in which trial information is reported pooled across the treatment groups.

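### The by-arm count of graded laboratory values ignores each participant's own baseline grade and is not split by grade, and the table shells have no place for Schedule 4 or repeat values

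*SAP*

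**What the plan says.** Laboratory measures are part of primary endpoint 1 (Protocol 3.1, SAP 2.1). SAP 7.1.3, which repeats Protocol 4.13.3.3, plans box plots and summary statistics by arm and timepoint, "as well as changes from baseline for postenrollment values". It also plans a number and percentage of participants with values at Grade 1 or above, which "will be tabulated by treatment arm for each postinfusion timepoint". Reportable laboratory abnormalities without a clinical diagnosis also enter the adverse event tables.

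SAP Appendix A opens with "Mock tables and figures for the DSMB Closed Report are included below", and SAP section 6 makes that appendix the specification of the closed report. Its Table 13B, titled "Safety Laboratory Values Meeting Grade 1 AE Criteria or Above, by Treatment Assignment", gives one count and percentage per analyte and arm in rows Infusion #1 to #10. It has no condition on the participant's baseline, no grade columns, no worst-grade row and no stated denominator. Table 13A uses the same visits and adds a baseline row, a median change from baseline, and the minimum and maximum. Figures 6 to 12 are box plots by infusion visit.

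On timing, Protocol Appendix J states: "Blood draws required at infusion visits must be performed prior to administration of study product". Infusion #1 is therefore a pre-dose value. Protocol 5.1 admits participants with ALT below 2.5 times, and creatinine up to 1.25 times, the upper limit of normal.

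Under Protocol 5.3.3, one reason for permanently stopping infusions is "Any grade 3 or 4 lab abnormality confirmed by a repeated value that is subsequently considered to be related to study product". Such participants are encouraged to continue on Schedule 4, for which Protocol 7.7 lists "Blood collection for HIV testing, PrEP monitoring, CBC/differential, ALT, creatinine, VRC01 Ab levels, functional assays, and sample storage". Appendix I places CBC, ALT and creatinine at Weeks 8, 32 and 56.

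**The concern.** Two features of the count make it a weak summary of new laboratory abnormality.

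First, each row mixes abnormalities that arose after dosing with those the participant brought into the trial. A persistent entry abnormality appears in row #1 and again in rows #2 to #10. Without a grade split, a Grade 1 and a Grade 4 value count the same. Protocol 2.9.4 describes the laboratory changes attributed to VRC01 so far as mild or moderate, and a low-grade shift is what such a count shows least clearly.

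Second, the shells follow infusion visits. Once infusions stop, the later Schedule 4 values and any repeat draws have no row, although SAP 7.1.3 speaks of every timepoint after infusion.

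At stake is how readily a monitoring board or a reader of the final report can see a modest laboratory signal in a component of a primary endpoint.

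**Working it through.** The plan states no figure for laboratory abnormality rates, so there is none to reproduce. The check is of the text, with an illustration under stated assumptions.

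**1. What one row measures.** Let b be the proportion at Grade 1 or above before the first dose, assumed equal in the arms and fully persistent. Let p be the new-onset proportion among participants normal at baseline.

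- Table 13B row: b + (1 − b)p
- New-onset count over all participants: (1 − b)p
- Difference between arms under either count: (1 − b)(p₁ − p₀)

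The b terms cancel in the difference. They do not cancel in the ratio, and they enlarge the binomial variance.

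**2. Numbers.** Arm size is 900 (Protocol 4.8). Assumed: p₁ = 3%, p₀ = 1%, and b = 2%, 5% or 10%. The documents give none of these rates. The standard error is √[(q₁(1 − q₁) + q₀(1 − q₀))/900], where q₁ and q₀ are the proportions shown in the table. Power is Φ(difference/SE − 1.96).

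| b | Table 13B row | Ratio | New-onset count | Ratio | Difference, both (points) | SE: row / new-onset (points) | Power if tested: row / new-onset |
|---|---|---|---|---|---|---|---|
| 2% | 4.94% vs 2.98% | 1.66 | 2.94% vs 0.98% | 3.0 | 1.96 | 0.92 / 0.65 | 57% / 85% |
| 5% | 7.85% vs 5.95% | 1.32 | 2.85% vs 0.95% | 3.0 | 1.90 | 1.19 / 0.64 | 36% / 84% |
| 10% | 12.7% vs 10.9% | 1.17 | 2.70% vs 0.90% | 3.0 | 1.80 | 1.52 / 0.63 | 22% / 82% |

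With assumed new onset of 6% versus 3%, the true ratio of 2.0 appears in the row as 1.60, 1.36 and 1.21 at b = 2%, 5% and 10%. The differences are 2.94, 2.85 and 2.70 points. The pattern is the same: the ratio shrinks and the difference barely moves.

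**3. Rows and visits.** In Schedule 1, safety laboratory tests are scheduled only at screening and infusion visits (Protocol Appendix F), so for participants still on infusions the shell rows follow collection. For those who stop, the scheduled Schedule 4 safety values left without a row are:

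| Last infusion-visit row with a value | Later rows without the participant | Schedule 4 safety values still scheduled |
|---|---|---|
| #2, #3, #4 | 8, 7, 6 | Weeks 32 and 56 |
| #5, #6, #7 | 5, 4, 3 | Week 56 |
| #8 or later | 2 or fewer | none |

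**4. Size of the row loss.** Suppose a later row should read 54/900 = 6.0%, and k of those 54 have stopped infusions and are still abnormal. The row then reads (54 − k)/900 with an enrolled denominator, or (54 − k)/(900 − k) with a values-available denominator. This gives 5.9% for k = 1, 5.6% for k = 4, 5.0% to 5.1% for k = 9, and 4.0% to 4.1% for k = 18. The documents give no basis for choosing k.

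**The case against.** The opposing case is substantial, and most of it stands.

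- Appendix A is a mock interim report, and SAP 7.1.3 does not restrict the count to infusion visits. This stands for the visit restriction, which is a mismatch to reconcile. It does not answer the missing baseline reference and grade split, which are absent from SAP 7.1.3 and Protocol 4.13.3.3 as well.
- Baseline is visible. Row #1 of Table 13B gives each arm's pre-dose prevalence, Table 13A gives change from baseline with minimum and maximum, and box-plot outliers are drawn. This stands at arm level. None of it shows how many participants have a new, persistent or worsened abnormality, and a median change hardly moves for a few raised values.
- Reportable abnormalities reach the adverse event tables over the whole study period. Tables 9 and 11 split by severity, Table 10 isolates Grades 3 to 5, Table 12 covers related events, and Table 6 lists reasons for stopping infusions. This stands. Those tables are by MedDRA class or term and not by analyte, and the documents do not show that every Grade 1 shift is reportable.
- The grading thresholds are in an external table, so whether an eligible entry value is Grade 1 cannot be settled from these documents. This stands, which is why b is an assumption.
- Putting Schedule 4 values into infusion-numbered rows would mix off-infusion with on-infusion values. This stands and shapes the fix.

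A reader might infer that Table 13B is biased toward no difference. The algebra above does not support that: the absolute difference is the same under both counts, and randomization balances baseline abnormality in expectation. A reader might also infer that an arm with more laboratory toxicity loses its affected participants from the safety record. That goes too far. The mandatory laboratory stop needs a confirmed, related Grade 3 or 4 value. A triggering value drawn at an infusion visit keeps its own row, and a reportable one is in the adverse event tables.

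**Conclusion.** The point holds as a modest, inexpensive improvement. The only planned by-arm count of graded laboratory values does not separate new or worsened abnormalities from pre-existing ones and does not separate grades. Under the assumed rates, a true ratio of 3.0 would appear as 1.66 to 1.17 for baseline prevalence of 2% to 10%. The standard error would be about 1.4 to 2.4 times that of a new-onset count, for an unchanged difference of 1.8 to 2.0 points. These figures assume full persistence and 900 per arm. The power figures are illustrative only, because the plan tests nothing in these tables.

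The Schedule 4 gap is real in the shells. Its effect is unknown and may be small: in the earlier trials summarised in Protocol 2.9.4, the laboratory changes attributed to product did not require stopping. No planned safety inference is invalidated.

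**What to change.** Add to Table 13B and SAP 7.1.3, for each analyte and arm, the number and percentage of participants whose worst grade after Infusion #1 is higher than their own Infusion #1 grade. Split the count by maximum grade (1, 2, 3, 4). Use all local values, including repeats and Schedule 4, with participants having at least one post-baseline value as the stated denominator.

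Align the shells of Tables 13A and 13B and Figures 6 to 12 with the timepoint wording of SAP 7.1.3. Show Schedule 4 values at Weeks 8, 32 and 56 as separately labelled rows or panels. The existing by-visit rows can stay.

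The cost is a few lines of SAP text and slightly more table programming. The values are already collected and graded, so no new data are needed.
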